Participants currently receiving the **Q3/4W** schedule of injections will be given the option to change to the **QW** schedule (Section 3.1.2).

Participants will be evaluated for key primary and secondary antitumor response endpoints based on RECIST 1.1. Additional primary endpoints include characterization of the immunologic response (eg, changes in CD8+ TIL levels and PD-L1 expression) to lerapolturev with and without anti-PD-1 and safety. Because lerapolturev is an immunotherapeutic, participant management with respect to treatment decisions (eg, confirmation of PD for study discontinuation) will occur based on iRECIST criteria. However, participants in the safety run-in or Arm 1 are allowed to crossover to Arm 2 upon RECIST-defined PD. ORR, DOR, and DRR based on iRECIST are exploratory endpoints.

Planned Number of Participants

Up to approximately 56 participants

Study Entry Criteria

Inclusion Criteria:

- 1. ≥ 18 years of age
- 2. Prior CDC-recommended vaccination series against poliovirus (PV), and has received a boost immunization with trivalent IPOL® (Sanofi-Pasteur SA) at least 1 week, but less than 6 weeks, prior to Day 1
 - a. NOTE: Patients who are unsure of their vaccination status must provide evidence of anti-PV immunity prior to enrollment, as applicable

Confidential Page 11 of 109

- 3. Has biopsy proven unresectable cutaneous melanoma and is willing to undergo tumor biopsy prior to the first dose of study drug(s) and at prespecified intervals during the study. Note the following details:
 - a. Patients with ocular, acral or mucosal melanoma are not eligible
 - b. Patients with M1c or M1d disease are NOT eligible
 - c. Submission of an archival biopsy sample is allowed in lieu of the baseline tumor biopsy, provided the tissue is ≤4 months old and the participant received no intervening systemic/intratumoral anti-cancer therapy since the biopsy was acquired.
 - d. Must have at least 1 lesion that is amenable to biopsy. The lesion must be safely accessible as determined by the investigator and should not be located at sites that require significant risk procedures to biopsy. Examples of sites considered to be of significant risk include but are not limited to the following: the brain, lung, mediastinum, pancreas, or endoscopic procedures extending beyond the esophagus, stomach, or bowel wall.
- 4. Has ≥ 2 melanoma lesions that are accurately measurable by caliper or a radiological method according to RECIST 1.1 criteria

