3.1.1 Crossover

Participants receiving lerapolturev monotherapy (Safety Run-In Cohort or Arm 1) may crossover to combination (lerapolturev and anti-PD-1) therapy if any of the following criteria are met

- radiologic disease progression per RECIST v1.1 (progression does not need to be confirmed prior to crossover)
- have not had progression or confirmed partial response per RECIST v1.1 by week 26 on study
- o partial response ≥ 6 months in duration

All participants crossing over to combination therapy should have a complete assessment of tumor burden (ie, scans and caliper/ruler measurement of skin lesions with photographic documentation) ≤ 28 days prior to starting the combination. The dose of lerapolturev administered in combination will be the same as monotherapy and is detailed in Table 7. The schedule of lerapolturev injections at the time of initiation of combination therapy will depend on the timing of crossover (Table 6).

Confidential Page 51 of 109

Table 6. Lerapolturev Injection Schedule After Crossover

Schedule of lerapolturev monotherapy injections at the time of crossover	Timing of when criteria for crossover are met	Recommended lerapolturev dosing schedule for combination
Participant is receiving weekly injections	< 6 months from Cycle 1 Day 1	Continue weekly injections for a total of 7 (monotherapy + combination) followed by every 3 week dosing (pembrolizumab) or every 4 week dosing (nivolumab)*
Participant is receiving injections every 3 weeks (pembrolizumab) or every 4 weeks (nivolumab)	< 6 months from Cycle 1 Day 1	Continue concurrent dosing schedule
Participant is receiving injections every 3 weeks (pembrolizumab) or every 4 weeks (nivolumab)	≥ 6 months from Cycle 1 Day 1	Weekly x 7 followed by every 3 week dosing (pembrolizumab) or every 4 week dosing (nivolumab)

*NOTE: Anti-PD-1 dosing begins Day 1 of crossover. Following the 7th weekly injection, lerapolturev should be administered Q3w when in combination with pembrolizumab (given Q3 or 6w), or Q4w when in combination with nivolumab (given Q2 or 4w).

3.1.2 Considerations for Modification of Dose and/or Dosing Schedule for Participants receiving the Q3/4W Schedule of Injections.

Lerapolturev Dose: All participants receiving lerapolturev on the **Q3/4W** schedule will have their lerapolturev dose adjusted as described in Section 5.3.

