9.1.5 Data and Safety Monitoring Committee

An external DSMC has been engaged to closely monitor the safety of the interventions under investigation during this study. The DSMC was tasked to review the data during (1) the safety run-in, (2) once 12 participants treated with the **Q3/4W** schedule were randomized and completed the DLT period (eg, after approximately six participants have been treated with lerapolturev plus anti-PD1 therapy), (3) at the previously planned interim analysis (IA) and (4) approximately every 4 months after the IA.

Confidential Page 85 of 109

As mentioned in Section 3.1, the DSMC met on 20 December 2021 to review all available safety data collected following clearance of the DLT monitoring period of the 12th participant randomized (all receiving Q3/4W schedule) (18 participants total: n=6 from the safety run-in and n=12 randomized [n=6 per arm]), as well as to discuss the feasibility of increasing the lerapolturev dose and changing the dosing schedule (ie, max dose of 1.6 x 10⁹ TCID₅₀ administered using the **QW** schedule). Given the favorable tolerability profile of lerapolturev, when given alone or in combination with anti-PD-1, the DSMC supported the Sponsor's recommendation to change the lerapolturev dose and schedule, with the agreement that the next DSMC meeting should occur once 12 participants (n=6 per arm) have received the **QW** lerapolturev dosing schedule and have cleared the DLT period. As before, the DSMC will make recommendations regarding whether adjustments to lerapolture dose are warranted, as well as whether to continue the study as planned. Based on this agreement with the DSMC and other logistical considerations, the DSMC will no longer meet to review data at the previously planned IA. Once the planned QW schedule safety evaluation is complete, the DSMC will continue to meet approximately every 4 months thereafter, as previously described.

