Participant is receiving weekly injections	< 6 months from Cycle 1 Day 1	Continue QW injections for a total of 7 (monotherapy + combination) followed by Q3W dosing (pembrolizumab) or Q4W dosing (nivolumab)*
Participant is receiving injections Q3W (pembrolizumab) or Q4W (nivolumab)	< 6 months from Cycle 1 Day 1	Continue concurrent dosing schedule

Schedule of lerapolturev monotherapy injections at the time of crossover	Timing of when criteria for crossover are met	Recommended lerapolturev dosing schedule for combination
Participant is receiving injections Q3W (pembrolizumab) or Q4W (nivolumab)	≥ 6 months from Cycle 1 Day 1	Weekly x 7 followed by every Q3W (pembrolizumab) or Q4W dosing (nivolumab)

After 12 participants have been treated under Study Protocol Amendment 4 (amendment that increased the lerapolturev dose and changed to QW injection schedule) and on study approximately 21 days (ie, once n=6 participants per treatment arm receiving lerapolturev QW have completed the dose-limiting toxicity (DLT) evaluation period), an additional safety review will be performed by the DSMC to confirm the safety of lerapolturev with or without anti-PD-1 and/or to make recommendations related to lerapolturev dose and/or schedule adjustments.

Participants receiving the Q3/4W schedule of injections are required to receive the increased lerapolturev dose and will be given the option to change to the QW schedule once Study Protocol Amendment 4 is open at their respective site.

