3. GENERAL STATISTICAL CONSIDERATIONS

3.1. SAMPLE SIZE AND POWER

The determination of sample size in this two-arm, randomized open-label Phase 2 trial was based on feasibility and logistical considerations. As discussed in Protocol Section 1.1, the Sponsor estimates that the true activity of anti-PD-1 re-challenge in the anti-PD-1 refractory population eligible for this study is less than 10%. Therefore, lerapolturev administered in combination with anti-PD-1 therapy using the QW injection schedule, will be considered to have anti-tumor activity in the anti-PD-1 refractory melanoma population if the lower bound of the 95% CI is above 10%. We estimate the sample size for participants receiving lerapolturev (QW schedule) ± anti-PD-1 therapy to be approximately 30 participants (n=15 per arm). Therefore, 5 of 15 participants (ie, 33%) in Arm 2 treated with the lerapolturev/anti-PD-1 combination (QW schedule) must have an objective response for the 95% CI to be greater than 10% (95% CI: 11.8% to 61.6%).

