5. STATISTICAL METHODS

Descriptive statistical methods will be used to summarize the data from this study. Unless stated otherwise, the term "descriptive statistics" refers to number of participants (n), mean, median, standard deviation, minimum and maximum for continuous data and frequencies and percentages for categorical data.

Survival endpoints will be analyzed with Kaplan-Meier method and summarized with median, twenty-fifth and seventy-fifth percentiles, and 95% confidence intervals (CI), if applicable.

All data collected during the study will be included in data listings. Unless otherwise noted, the data will be sorted first by treatment, participant, and then by date within each participant number.

All summary tables and figures will be presented by treatment group and overall. The term "treatment group" refers to the following subgroups:

- lerapolturev monotherapy on the QW schedule
- lerapolturev monotherapy on the Q3/4W schedule
- lerapolturev + anti-PD-1 on the QW schedule
- lerapolturev + anti-PD-1 on the Q3/4W schedule
- all crossover to lerapolturev + anti-PD-1 participants
- lerapolturev + anti-PD-1 plus crossover participants (all lerapolturev + anti-PD-1)
- overall treated participants

Analyses will be implemented using SAS® 9.4 or higher (SAS Institute, Cary, North Carolina, USA). The International Conference on Harmonization (ICH) numbering convention (ie, ICH-E3) will be used for all tables and listings. Upon completion, all SAS® programs will be validated by an independent programmer within the staff of the third-party vendor doing the primary analysis. The validation process will be used to confirm that statistically valid methods have been implemented and that all data transformations and calculations are accurate. Checks will be made to ensure accuracy, consistency with this plan, consistency within tables, and consistency between tables and corresponding data listings. All documents will be verified by the lead statistician to ensure accuracy and consistency of analyses.

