5.7.1. Adverse Events

AE will be mapped to a MedDRA version 24.0 by SOC and PT. If a participant experiences multiple events that map to a single PT, the greatest severity and strongest assessment of relation to a study drug will be assigned to the PT for the appropriate summaries. AE severity will be assessed according to the NCI CTCAE version 5. If CTCAE grading does not exist for an AE, the severity of the AE will be graded as mild (1), moderate (2), severe (3), life-threatening (4), or death (5).

AESIs will be identified within the EDC by the investigator.

The number of participants for the following groups will be summarized by treatment group and overall:

- Any TEAE
- Any TEAE related to
 - o lerapolturev

- o anti-PD-1 therapy
- Any TESAE
- Any TESAE related to
 - o lerapolturev
 - o anti-PD-1 therapy
- Any treatment-emergent lerapolturev AESIs
- Any treatment-emergent irAEs
- Any TEAE with CTCAE grade ≥ 3
- Any TEAE related to
 - o lerapolturev with CTCAE grade ≥ 3
 - o anti-PD1 therapy with CTCAE grade ≥ 3
- Any Grade 5 TEAE
- Any Grade 5 TEAE related to lerapolturev or anti-PD1 therapy

The occurrence of TEAEs and TEAEs related to lerapolturev, or anti-PD-1 therapy will be summarized by PT, SOC, and severity. Additionally, TEAEs will be summarized by PT in descending frequency. All AEs reported will be listed for individual participants showing both verbatim and PT. All AEs that occurred prior to initiation of study drugs will be excluded from the tables but will be included in the listings.

Adverse events occurring during screening due to lerapolturev-related procedures that are not standard of care (eg, PV booster) will be considered related to lerapolturev and summarized separately.

Additional analysis may be conducted to investigate rates of TEAE based on lerapolturev dose and/or schedule. Should there be a difference, we may perform additional analyses to discern whether there is a relationship between dose and occurrence of AEs.

Missing onset dates will be imputed as previously outlined in Section 3.2.3.2 as required to determine TEAE.

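### AE tables always produced are split by schedule and never by dose, although Q3/4W participants had to move to the higher dose; the only dose-AE analysis is optional and hangs on an undefined difference

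*SAP*

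**What the plan says.** SAP 5.7.1 contains a two-step provision. Step one is optional: "Additional analysis may be conducted to investigate rates of TEAE based on lerapolturev dose and/or schedule". Step two is conditional on step one and again optional: "Should there be a difference, we may perform additional analyses to discern whether there is a relationship between dose and occurrence of AEs". Neither sentence defines a difference.

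The AE summaries that are always produced use the treatment groups of SAP 5, for example "lerapolturev monotherapy on the Q3/4W schedule". Those groups are monotherapy and combination, each by QW and Q3/4W, then all crossover participants, all combination including crossover, and overall. None is defined by dose, and the crossover column is not split by schedule or dose.

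On dose, SAP 1.1 states: "Participants receiving the Q3/4W schedule of injections are required to receive the increased lerapolturev dose". Only the change of schedule is left to choice. Protocol 3.1.2 agrees that all participants on Q3/4W "will have their lerapolturev dose adjusted as described in Section 5.3".

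SAP 4.3 and 5.7 attribute safety data to the treatment at the time of assessment when a participant crosses from monotherapy to combination. They give no such rule for the dose increase or for a move from Q3/4W to QW. Under Protocol 8.4 a participant who switches schedule meets the definitions of both schedule-specific safety populations.

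**The concern.** Safety is a primary objective, and Amendment 4 raised dose and injection frequency together on the stated expectation (Protocol 1.3.2 and 1.3.3) that toxicity would not rise materially. The natural check is to compare AEs under the old and new regimens. The standing tables cannot do this cleanly. An AE that starts under the new maximum in someone still on Q3/4W is counted in the Q3/4W column, beside AEs from the old dose. If the higher dose causes AEs, this raises the Q3/4W rate and narrows the visible gap to QW. The one provision that could separate dose from schedule may never be carried out, and has no rule for assigning an AE to a dose if it is. A quiet comparison in small, mixed columns could then be taken as reassurance about dose.

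**Working it through.** **1. The plan's own figure.** The only precision statement in SAP 3.1 is the exact 95% CI for 5 responses in 15. Clopper-Pearson: lower = Beta(0.025; 5, 11) = 11.8%; upper = Beta(0.975; 6, 10) = 61.6%. This reproduces. No power or precision is stated for any AE comparison.

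**2. Inputs.**
- QW: about 15 per arm, about 30 in total (SAP 3.1).
- Q3/4W: 18 by 20 December 2021 (Protocol 9.1.5), that is 6 run-in + 6 Arm 1 = 12 monotherapy and 6 combination. Upper end: the protocol synopsis plans "Up to approximately 56 participants", and 56 − 30 = 26.
- Base rate: 6/17 = 35.3% with a lerapolturev-related AE at 10 December 2021 (Protocol Table 4). Its exact 95% CI is 14.2% to 61.7%.
- Doses per visit: 1 to 6 x 10^8 TCID50 in the run-in (Protocol 3.1). From Protocol 5.3, the new range runs from 0.5 ml x 5.33 x 10^8 = 2.67 x 10^8 to 3 ml x 5.33 x 10^8 = 1.6 x 10^9. The two ranges overlap between 2.67 and 6 x 10^8.

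**3. Precision, as an illustration.** Power = sum over all outcome pairs (a, b) of Bin(a; n1, p1) x Bin(b; n2, p2) for which the two-sided Fisher p-value is at most 0.05. The test is my assumption; the SAP names none. For a true rise from 35% to 60%:

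| Comparison (Q3/4W vs QW) | Power |
|---|---|
| Monotherapy, 12 vs 15 | 18% |
| Combination, 6 vs 15 | 12% |
| Pooled, 18 vs 30 | 34% |
| Pooled, 26 vs 30 | 39% |

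The pooled rows combine monotherapy with combination, which SAP 5 does not do; they are the favourable case. A much larger rise, from 35.3% to 75.3%, reaches 74% at 18 vs 30.

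**4. Effect of the mixed column.** Let f be the share of the Q3/4W column that shows the higher-dose rate. The column rate is p0 + f(p1 − p0). The documents do not give f. Taking f = 1/3 (range 1/6 to 1/2), with p0 = 35% and p1 = 60%, the column rate is 35 + 25/3 = 43.3% (39.2% to 47.5%). The 25-point gap shrinks to 16.7 points (20.8 to 12.5), and power at 18 vs 30 falls from 34% to 16% (24% to 10%). This assigns the whole rise to dose. Any part caused by weekly injection is not diluted in this way.

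**5. What the trigger does if read descriptively.** Same groups (12 vs 15, 6 vs 15, 18 vs 30), base 35.3%, no dilution:

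| Meaning of a difference | Opens with no effect | Opens with +25 points |
|---|---|---|
| Any numerical difference | 93% to 97% | 97% to 99% |
| QW higher by at least 20 points | 9% to 22% | 62% to 65% |

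The first reading opens almost always, effect or not. The second misses more than a third of true 25-point rises. How the trigger behaves therefore depends on a definition the SAP does not give.

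**The case against.** The strongest reply is that the plan is descriptive. SAP 5 says so, and Protocol 8.3 rules out formal hypothesis tests for the schedule comparisons. A reader might infer from the Fisher figures that a real dose effect will usually be missed, for instance in 100 − 34 = 66% of trials at 18 vs 30. The documents do not support that. They set no significance test as the trigger, and if any numerical difference counts, the trigger opens nearly every time. A reader might also infer that the first look must use the mixed schedule columns, or that the SAP treats no visible difference as proof of no dose effect. It says neither: step one may be done by dose itself, and no conclusion is attached to a null look.

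Much is also in place. TEAEs, related TEAEs and Grade 3 or higher TEAEs are tabulated unconditionally by schedule group. TCID50 per cycle and in total is summarised (SAP 5.5). Injections and AEs are listed by participant. The DSMC reviews the first 12 QW participants after the DLT period against a 33% limit. Protocol 8.5.3 requires no dose-AE analysis.

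All of this stands, and it limits the point. It leaves three gaps: the Q3/4W columns contain the higher dose, no rule assigns an AE to the dose in force at onset, and no planned table links dose received to AEs.

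**Conclusion.** The point holds as a weakness in how AEs are displayed and attributed. The standing AE tables cannot separate the old dose from the new, because both documents put the increased dose inside the Q3/4W columns and events are divided only at crossover to combination. The crossover column is split by neither dose nor schedule. The provision that could repair this is optional at both steps and rests on an undefined difference.

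The size cannot be given as a miss rate. The 34% (39% with 26 on Q3/4W) is an illustration of low precision. It rests on an assumed Fisher test, the December 2021 counts, the planned QW size and a 35% base rate whose own interval is wide. The dilution figures rest further on an assumed f. What follows is limited but firm: with these numbers, seeing no difference says little about whether dose affects toxicity, and the report should not suggest otherwise. This is a cheap improvement to the plan and not a threat to its primary response analysis.

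**What to change.** Replace the two conditional sentences in SAP 5.7.1 with an unconditional descriptive table of TEAEs, lerapolturev-related TEAEs and Grade 3 or higher TEAEs. Classify each AE by the dose period (before or after that participant's Amendment 4 dose increase) and by the schedule in force at onset. Split a participant's time at each dose or schedule change, as the SAP already does by treatment at crossover, and apply the same split within the crossover column. Give exposure-adjusted rates with 95% CIs.

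Add a summary of AEs by TCID50 actually received, per visit and cumulative. Dose period alone is a coarse measure, because a participant under the new maximum can receive less than one did under the old.

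Label both displays non-randomised and confounded with time on treatment, the eligibility changes of Amendment 4, and schedule. Word conclusions from the intervals, stating which increases are not excluded.

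The cost is one SAP paragraph and one or two tables, built from injection dates, doses and AE dates already collected. The intervals will be wide, and the text should say so. Treatment, visits and data collection do not change.

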5.7.2. Clinical Laboratory Assessments

AEs for clinical labs will be characterized according to NCI CTCAE version 5 (when possible) and shift in grade from baseline to the worst post-baseline value will be summarized. Both scheduled and unscheduled assessments will be used to identify the worst post-baseline values.

The following categories of abnormal hepatic laboratory values will be evaluated for any occurrence among all post baseline assessments.

- Alanine Aminotransferase (ALT) and/or Aspartate Aminotransferase (AST) > 3 x ULN, Alkaline Phosphatase (ALP) < 2 x ULN, and Total Bilirubin ≥ 2 x ULN
- AST > 3, 5, 8, 10, and 20 x ULN, and 5 x ULN for more than 5 weeks
- ALT > 3, 5, 8, 10, and 20 x ULN, and 5 x ULN for more than 5 weeks
- Total Bilirubin > 1.5 or ≥ 2 x ULN

Listings of all laboratory data with normal reference ranges and NCI CTCAE grades (when possible) will be provided.

5.7.3. Vital Signs

For vital sign parameters (systolic blood pressure, diastolic blood pressure, heart rate, respiratory rate, body temperature, and weight), the observed values and change from baseline will be

summarized using descriptive statistics at each visit. The maximum post-baseline values and the change from baseline will also be summarized. Both scheduled and unscheduled assessments will be used to identify the worst post-baseline values.

A listing of all vital sign data will be provided.

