12 APPENDIX I

ASTCT Consensus Grading for CRS adapted from Lee et al., 2019⁴¹

CRS Parameter	Grade 1	Grade 2	Grade 3	Grade 4	Grade 5
Fever ¹	Temperature ≥38°C	Temperature ≥38°C	Temperature ≥38°C	Temperature ≥38°C	
		With	า		Death due to CRS, where another factor is
Hypotension	None	Not requiring vasopressors	Requiring a vasopressor with or without vasopressin	Requiring multiple vasopressors (excluding vasopressin)	
	And/or ²				
Hypoxia	None	Requiring low-flow nasal cannula ³ or blow-by	Requiring high-flow nasal cannula ³ , facemask, nonrebreather mask, or Venturi mask	Requiring positive pressure (eg, CPAP, BiPAP, intubation and mechanical ventilation)	not the principle cause

Organ toxicities associated with CRS may be graded according to CTCAE v5.0, but do not influence CRS grading.

- Fever is defined as temperature ≥38°C not attributable to any other cause. In patients who have CRS then receive antipyretic
 or anticytokine therapy such as tocilizumab or steroids, fever is no longer required to grade subsequent CRS severity. In this
 case, CRS grading is driven by hypotension and/or hypoxia.
- 2. CRS grade is determined by the more severe event: hypotension or hypoxia not attributable to any other cause. For example, a patient with temperature of 39.5°C, hypotension requiring 1 vasopressor, and hypoxia requiring low-flow nasal cannula is classified as grade 3 CRS.
- 3. Low-flow nasal cannula is defined as oxygen delivered at ≤6 L/minute. Low flow also includes blow-by oxygen delivery, sometimes used in pediatrics. High-flow nasal cannula is defined as oxygen delivered at >6 L/minute.

ASTCT Consensus Grading for ICANS adapted from Lee et al., 2019⁴¹

Neurotoxicity Domain	Grade 1	Grade 2	Grade 3	Grade 4	Grade 5
ICE score ¹	7 to 9	3 to 6	0 to 2	0 (patient is unarousable and unable to perform ICE)	
Depressed level of consciousness ²	Awakens spontaneously	Awakens to voice	Awakens only to tactile stimulus	Patient is unarousable or requires vigorous or reptitive tactile stimuli to arouse. Stupor or coma	Death due to ICANS
Seizure	N/A	N/A	Any clinical seizure focal or generalized that resolves rapidly or nonconvulsive seizures on EEG that resolve with intervention	seizure (>5min); or repetitive clinical or electrical seizures without return to baseline in between	
Motor findings ³	N/A	N/A	N/A	Deep focal motor weakness such as hemiparesis or paraparesis	

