3.2.4. Presentations by Study Visit

When data are collected serially over time, individual data presentations may include by-study visit displays. By-study visit displays will only be summarized up to 30 days after last treatment. Visits will be presented according to the nominal visit as obtained from the eCRF. If multiple observations are collected at a scheduled visit, the closest observation to the target day will be chosen. If two observations have equal distance from the target day but one is earlier and the other is later than the target day, the earlier observation will be chosen. Unscheduled assessments will be included in the listings.

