3.2.5. Presentations by Worst Case

When data are collected serially over time, individual data presentations may include "worst case on study" displays. In those situations, both scheduled and unscheduled assessments up to 30 days after last treatment will be included.

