5.7. SAFETY

Participants receiving at least one lerapolturev injection will be analyzed for safety. Values for all safety variables will be listed by participant and visit (as applicable). Safety summaries by visit will use scheduled visits up to 30 days after the last dose of study drugs.

If a participant crosses over from monotherapy to combination therapy, then the treatment analyzed will be based on the treatment for that participant at the time of the assessment.

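### The across-visit worst-case summary of vital signs names only the maximum, so each participant's lowest blood pressure and weight, and the largest fall in each, are not summarised

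*SAP*

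**What the plan says.** SAP 5.7.3 covers systolic and diastolic pressure, heart rate, respiratory rate, temperature and weight. It plans three outputs.

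- By visit: observed values and change from baseline, "summarized using descriptive statistics at each visit". SAP 5 says that the term descriptive statistics "refers to number of participants (n), mean, median, standard deviation, minimum and maximum for continuous data".
- Across visits: "The maximum post-baseline values and the change from baseline will also be summarized". The sentence after it reads "Both scheduled and unscheduled assessments will be used to identify the worst post-baseline values".
- A listing of all vital-sign data.

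Two general rules decide which readings enter the tables. For by-visit safety output, SAP 5.7 states "Safety summaries by visit will use scheduled visits up to 30 days after the last dose of study drugs", and SAP 3.2.4 adds "Unscheduled assessments will be included in the listings". For worst-case displays, SAP 3.2.5 states that "both scheduled and unscheduled assessments up to 30 days after last treatment will be included". SAP 3.2.5 does not say in which direction worst is to be read.

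The table list in SAP 11 has one vital-sign table, 14.3.4.5, titled as a by-visit summary. Change in vital signs is an endpoint under the primary safety objective (Protocol 2.1, SAP 2).

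**The concern.** The across-visit summary exists to show extremes, and it is the only tabulated vital-sign output that uses unscheduled readings. As written it has one direction for every parameter. That direction suits temperature. It does not suit a fall in blood pressure or a loss of weight, where the maximum is the participant's highest reading.

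Downward changes in pressure are of interest in this trial. Protocol 1.3.1 describes a theoretical risk of CRS when the virus is given with anti-PD-1 and commits to monitoring for it. Protocol 9.2 lists hypotension among its signs, and Protocol Appendix I states "CRS grade is determined by the more severe event: hypotension or hypoxia not attributable to any other cause". In that grading table, fever is the same at Grades 1 to 4, and hypotension and hypoxia separate the grades. A safety reader would therefore expect the worst-case summary to show how far each participant's pressure fell.

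**Working it through.** No figure in the plan is at issue, so the check sets the provisions side by side.

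**1. What the across-visit summary delivers.** Take a participant with baseline b and post-baseline values x1, ..., xk. The summary gives max(x). Its change from baseline can be read as the change at the maximum, max(x) − b, or as the maximum change, max(x − b). Because b is a single fixed value (SAP 3.2.6), these are the same number. The largest fall is min(x) − b, which neither reading supplies.

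Illustration with assumed values, not taken from the documents: baseline systolic pressure 130 mmHg, then 128, 82 and 126.

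- Maximum: 128, change 128 − 130 = −2.
- Minimum: 82, change 82 − 130 = −48.

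The planned across-visit summary reports 128 and −2 for this participant.

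**2. What the by-visit table recovers.** Descriptive statistics include the minimum. If the 82 was recorded at a scheduled visit, that visit's group minimum is 82 or lower, and the minimum change is −48 or lower. The fall is then visible. The statistic is one extreme per treatment group per visit, however. It does not give the distribution of participants' own lowest values or largest falls.

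**3. What happens to an unscheduled reading.** By-visit safety summaries use scheduled visits (SAP 5.7), and unscheduled assessments go to the listings (SAP 3.2.4). The across-visit summary admits unscheduled readings but takes the maximum. If the 82 was unscheduled, it is in the listing and in no vital-sign table.

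**4. Why scheduled readings do not fully cover this.** In both schedules of assessments (Protocol Tables 1 and 2, SAP Tables 2 and 3), on-treatment vital signs fall on lerapolturev injection days: Days 1, 8 and 15 of Cycles 1 and 2, also Day 22 of Cycle 1 with nivolumab, then Day 1 of each later cycle. Footnote 3 to each schedule places same-day assessments before treatment. Scheduled dosing-day readings are therefore pre-dose, and a fall in the hours after an injection would more naturally be caught at an unscheduled assessment.

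**5. Other routes into the tables.**

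- Protocol 9.2 counts a clinically significant abnormal vital-sign measurement, including worsening from baseline, as an adverse event. Such an event is tabulated under SAP 5.7.1.
- CRS is counted as an adverse event of special interest (SAP 5.7.1, Table 14.3.3.1). Protocol 9.2 has it recorded under the single CRS term, so its hypotension component is not tabulated separately.

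Both routes depend on the investigator's judgement. Neither summarises measured pressure.

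**The case against.** A reader might infer that vital signs are summarised by the maximum alone, that falls in pressure are never tabulated, or that the safety tables could not show hypotension. The SAP does not support any of these. By-visit summaries of both value and change include the minimum, every reading is listed, and the adverse-event tables are a further route. In a trial of up to approximately 56 participants the listing can be read in full.

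The CRS argument can also be pushed too far. The protocol speaks of a theoretical risk and does not call CRS the main safety concern. Fever is the required sign and tachycardia is another, and for both the maximum is the right extreme. Appendix I grades hypotension by vasopressor need, so a row of minimum systolic pressure would not grade CRS.

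Finally, the endpoint is change in vital signs, with no worst-case statistic required, and the wording may simply be loose. The sentence about worst values also appears in the laboratory section (SAP 5.7.2), where the CTCAE grade determines what is worst.

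All of this stands and limits the point. It does not remove it. The SAP chose to provide an across-visit extreme, called it the worst value, and named the maximum for parameters where that choice misses a fall. No other vital-sign table takes in an unscheduled low.

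**Conclusion.** The point holds in a narrow form. For systolic pressure, diastolic pressure and weight, each participant's lowest post-baseline value and largest decrease across visits are not summarised. Falls appear as group minima at scheduled visits and in the listing, and an unscheduled low reading reaches no vital-sign table.

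The number of participants affected is unknown, because it depends on how many low readings occur and how many are unscheduled. The conclusion assumes that the text of 5.7.3 is programmed as written. A programmer who read worst by direction would close the gap, but the SAP gives no such instruction. Efficacy conclusions are untouched. The matter is minor: a desirable correction to the reporting of a primary safety endpoint.

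**What to change.** In SAP 5.7.3 and the shell for Table 14.3.4.5:

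- State for each parameter whether worst means highest, lowest or both.
- Add the minimum post-baseline value and the largest decrease from baseline for systolic pressure, diastolic pressure and weight, using scheduled and unscheduled assessments within the 30-day limit of SAP 3.2.5.
- Retain the existing maximum summaries for every parameter, including blood pressure. Protocol 1.2.2.2 lists hypertension (11.8%) among the most common adverse events so far, so the upward direction still matters.

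The cost is two added quantities for each of three parameters: a few table rows from data already collected, with no change to study conduct.
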